In accordance with the EMA recommendations on the clinical investigation of human normal immunoglobulin for intravenous administration (*Guideline on the clinical investigation of human normal immunoglobulin for intravenous administration (IVIg), EMA/CHMP/BPWP/94033/2007 rev. 4, 16 Dec 2021*) the obtained results will be compared with literature data The conclusion of non-inferiority of the drug Bioven, solution for infusions 10%, in the treatment of chronic immune thrombocytopenia, will be made according to the main efficacy variable using an approach based on confidence intervals.

To do this, the calculated limits of the 95% confidence interval (CI) for the difference in the percentage of positive results according to the main variable ("the drug is effective") for the studied group must be compared with the limit of the non-inferiority zone - effectiveness that is not inferior (-25%) to the calculated based on data for comparison. If the lower limit of the CI is greater than the lower limit of the non-inferiority zone (non-inferiority), then it will be considered that the study drug is not inferior in effectiveness compared to literature data. A detailed description of statistical analysis is provided in the corresponding section of this Protocol.

Examination methods:

Examination methods are performed according to the schedule of events provided in the relevant section of the Protocol of this clinical trial.

- Collection and recording of demographic data;
- Collection and recording of medical history;
- Verification of ITP diagnosis (according to primary documentation);
- Recording information about previous ITP therapy (dose/schedule, duration, response (if any), and time interval since the last administration);
- Recording information about symptomatic therapy and medication intake for the treatment of concomitant diseases;
- Transfusion history;
- History of allergies;
- Determination of body weight;
- Objective physical examination with mandatory assessment of the severity of hemorrhagic syndrome;

| Bioven | |
|----------------------------|--|
| Trial Code: 2021-BV-ITP-BP | |

| - Measurement of vital signs (blood pressure, heart rate, respiratory rate, body | |
|---|--|
| temperature); | |
| - Biomaterials sampling for laboratory tests is carried out at collection points or by mobile | |
| team of the Central Laboratory designated by the Sponsor: | |
| - Blood test for HIV and RW, PCR EBV, CMV; | |

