10 STATISTICS

10.1 Content of statistical analysis

The null hypothesis for the primary efficacy endpoint H0: $p-p_0 \leq \delta$, where clinical effectiveness p is the proportion of patients who responded to therapy with the study drug BIOVEN; p_0 - proportion of patients responding to therapy according to literature data: δ - the limit of the difference of proportions without clinical significance. An alternative hypothesis H1: $p-p_0 > \delta$ («non-inferiority study» according to the guideline EMA «Points to consider on switching between superiority and non-inferiority» CPMP/EWP/482/99, London, 27 July 2000 Ta EMA "ICH Topic E 9 Statistical Principles for Clinical Trials" CPMP/ICH/363/96).

According to the EU recommendations on clinical studies of immunoglobulin normal for intravenous administration (Guideline on the clinical investigation of human normal immunoglobulin for intravenous administration (IVIg), EMA/CHMP/BPWP/94033/2007 rev. 3, 28 June 2018) the obtained results will be compared with literature data.

To test the null hypothesis, a two-tailed test will be used, based on the principles of estimating a 95% confidence interval for the difference in proportions and comparing it with the lower limit of equivalence (at a significance level of α 5%). For non-inferiority research, the null hypothesis is rejected if the conditions are met:

$$\sqrt{n(p-p_0-\delta) / p^{(1-p^{-})} > z_{\alpha/2}}$$

or
 $(p-p_0-\delta) / \sqrt{(\frac{p(1-p)}{n} + \frac{p_0(1-p_0)}{n_0})} > z_{\alpha/2}$

Confidence intervals of the difference will be calculated according to the generally accepted Wald method:

$$(p_1 - p_2) \pm z_{\alpha/2}^* \sqrt{(\frac{p_1(1 - p_1)}{n_1} + \frac{p_2(1 - p_2)}{n_2})}$$

The number of patients for the portion taken from literature sources is taken from the 2020 publication and will be 82 [Parodi E, Russo G, Farruggia P, Notarangelo LD, Giraudo MT, Nardi M, et al. Management strategies for newly diagnosed immune thrombocytopenia in Italian AIEOP Centres: do we overtreat? Data from a multicentre, prospective cohort study. Blood Transfus. 2020;18(5):396.]

Methods of descriptive statistics (for categorical variables - number and part in %, for quantitative variables - n, arithmetic mean, median, standard deviation, minimum and maximum), including construction of graphs and charts, methods of interval estimation (calculate of 95% confidence intervals for proportions and differences of fractions).

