scheme is recommended by the EMA and this Protocol, the total number of patients in the group is 82, the effectiveness of the use of IVIG in the treatment of ITP is indicated - 78% [Parodi E, Russo G, Farruggia P, Notarangelo LD, Giraudo MT, Nardi M, et al. Management strategies for newly diagnosed immune thrombocytopenia in Italian AIEOP Centres: do we overtreat? Data from a multicentre, prospective cohort study. Blood Transfus. 2020;18(5):396.]. According to our data and data from the literature, immunoglobulin belongs to drugs with a highly variable efficiency of 20-25%. Therefore, for a non-inferiority study, we consider it appropriate to set δ (the limit of the difference in efficiency between the obtained and expected results) at the level of -25%.

Thus, for a significance level of 5% and a statistical power of 80%, the effectiveness of the drug in the comparison model reaches 78%, the limit of the difference in specific weights (difference in effectiveness) without clinical significance δ is - 0.25. Then the calculation of the minimum sample size will look like this:

 $n = (1,96+1,28)2 \times (0,78 \times (1-0,78) / (0,78 - 0,78 + 0,25)^2 = 29$

Considering the risk of dropping out of patients for various reasons (20%), 36 patients will be included in the study.

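### The Wald interval that decides non-inferiority sets its lower limit too high at 26 to 40 patients: one-sided error is about 2.8–3.2% instead of 2.5%, and at 29, 32 or 40 analysed patients it passes with one responder fewer than a Miettinen-Nurminen interval

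*Combined protocol and SAP*

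**What the plan says.** Section 10.1 sets the framework: "a two-tailed test will be used, based on the principles of estimating a 95% confidence interval for the difference in proportions". It then names the interval, "Confidence intervals of the difference will be calculated according to the generally accepted Wald method", and prints the formula, a two-sample interval with unpooled variance. The second sample is the literature group: "The number of patients for the portion taken from literature sources is taken from the 2020 publication and will be 82".

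The decision rule is in the synopsis (Conclusion on efficacy) and again in 10.3.7. The drug is declared non-inferior "If the lower limit of the CI is greater than the lower limit of the non-inferiority zone". Section 10.2 chooses to "set δ (the limit of the difference in efficiency between the obtained and expected results) at the level of -25"%. Its sample size is justified "for a significance level of 5% and a statistical power of 80%, the effectiveness of the drug in the comparison model reaches 78"%, giving 29 evaluable patients. It continues: "Considering the risk of dropping out of patients for various reasons (20%), 36 patients will be included in the study". The synopsis and section 4.1 give a total of 40. Under section 10.4 efficacy is analysed in the per-protocol set, so the analysed number can be smaller than the number enrolled.

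No score-based, exact or continuity-corrected interval for the difference is planned, even as a sensitivity analysis.

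**The concern.** The Wald standard error is computed from the observed response rate. A result close to the decision line has an observed rate of about 70–72%, where p(1-p) is 0.20–0.21. At the null rate of 53% (78% less 25 points) p(1-p) is 0.25. The distance from the estimate down to the lower limit is therefore too short, and that distance is the only part of the interval that decides anything.

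The trial has a single arm, so this one limit carries the whole non-inferiority claim. If the interval does not deliver the 2.5% it implies on the deciding side, a borderline result can pass because of the formula. An assessor who recomputes it with a standard score method could then reach the opposite conclusion.

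**Working it through.** **Inputs.** Margin -0.25, reference rate 0.78, planning assumption p = p0 = 0.78, 29 evaluable and 36 included (10.2); n0 = 82, two-sided 95% interval and Wald formula (10.1); total of 40 (synopsis, 4.1). Assumption: the literature responder count is 64, because 0.78 × 82 = 63.96 and no count is given.

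**The plan's own figure.** (1.96 + 1.28)² × 0.78 × 0.22 / 0.25² = 10.4976 × 0.1716 / 0.0625 = 28.82, so 29 reproduces. 29/0.8 = 36.25, stated as 36. Applying the same 20% loss to the total of 40 gives 32.

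**Wald limit at 21/29.** p = 0.7241, p0 = 64/82 = 0.7805, difference -0.0563.
Variance = 0.7241 × 0.2759/29 + 0.7805 × 0.2195/82 = 0.00689 + 0.00209 = 0.00898; SE = 0.0947.
Lower limit = -0.0563 - 1.96 × 0.0947 = -0.242. Pass.

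**Miettinen-Nurminen at 21/29.** The rates are re-estimated under the constraint p - p0 = -0.25, giving 0.565 and 0.815.
Variance = (0.565 × 0.435/29 + 0.815 × 0.185/82) × 111/110 = 0.01041; SE = 0.1020.
z = (-0.0563 + 0.25)/0.1020 = 1.90, below 1.96. Fail (lower limit -0.257).

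**Wald limit at 28/40.** Difference 0.7000 - 0.7805 = -0.0805; SE = √(0.21/40 + 0.00209) = 0.0857; lower limit -0.248. Pass. Miettinen-Nurminen gives -0.256. Fail.

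**Smallest passing responder count against 64/82.**

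| n | Wald | Miettinen-Nurminen |
|---|---|---|
| 29 | 21 | 22 |
| 32 | 23 | 24 |
| 36 | 26 | 26 |
| 40 | 28 | 29 |

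Across n = 26 to 40 the one-responder gap occurs at 26, 29, 32, 35 and 40, which is 5 of 15 sizes.

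**Exact error and power.** Both samples were enumerated as binomials: error = Σ P(X=x | n, 0.53) × P(Y=y | 82, 0.78) over all (x, y) that pass, and power is the same sum with 0.78 for the trial arm.

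| n | Wald error | Miettinen-Nurminen error | Wald power | Miettinen-Nurminen power |
|---|---|---|---|---|
| 29 | 3.05% | 2.51% | 77.7% | 72.3% |
| 36 | 2.99% | 2.42% | 83.5% | 80.2% |
| 40 | 2.79% | 2.41% | 86.3% | 83.6% |

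Over n = 26 to 40 the Wald error is about 2.8–3.2% throughout; Miettinen-Nurminen stays between about 2.3% and 2.6%.

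**Newcombe as an alternative.** It also fails 21/29 (-0.253) and 28/40 (-0.252), and its error is 2.52% at n=29. At n=36 it is 2.78% and at n=40 it is 2.76%, almost the same as Wald's 2.79% at n=40.

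**The case against.** The strongest reply is that the effect is small. The excess error is well under one percentage point, the method and its formula are pre-specified, and at any size where the methods disagree they do so on a single responder count. At n=29, with the literature result held at 64/82, the chance of landing on exactly 21 is 2.65% - 1.00% = 1.65% at a true 53%. All of that stands and limits how serious the point is. It does not remove it: at a true 78% the chance of exactly 21/29 is 83.05% - 70.29% = 12.8%, so a disputed result is a realistic outcome.

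A second reply is that the literature result is already fixed. Holding it at 64/82 and taking 53% as the exact null, the Wald thresholds give errors of 2.65% (21/29), 1.48% (26/36) and 2.18% (28/40). But that treats 78% as known. The interval chosen in 10.1 counts the 82 patients as a sample, so the error over both samples is the matching yardstick.

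A reader might also infer stronger claims that the documents do not support:

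- *The Wald interval is too narrow overall.* It is not. At 21/29 its total width is 0.371, against 0.367 for Miettinen-Nurminen and 0.360 for Newcombe. The fault is in where the lower limit lies.
- *The verdict changes whatever the size.* It does not change at n=36, the enrolment in 10.2, or at most other sizes from 26 to 40.
- *The one-sample condition in 10.1 shows a larger Wald error.* That condition does not use the interval for the difference, and which condition applies is a separate question. Against a fixed 78%, Wald and Wilson need the same counts at 29, 36 and 40 (21, 25 and 28).
- *Secondary proportions will have zero-width intervals.* Section 10.1 assigns Wald only to the difference. Sections 10.1 and 10.3.3 promise 95% intervals for proportions without naming a method.

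**Conclusion.** The point holds in a limited form. The planned interval does not deliver the one-sided 2.5% implied by its two-sided 95% level: the error is about 2.8–3.2% for 26 to 40 patients, and a standard score method restores it to about 2.5%. Results of 21/29, 23/32 and 28/40 would be declared non-inferior under Wald and not under Miettinen-Nurminen. At n=36 the verdict against 64/82 is the same either way, although the error over both samples is still 2.99%.

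This should be corrected before analysis but does not by itself undermine the trial. It rests on three assumptions: 64 responders among the 82 literature patients, the boundary rates 53% and 78%, and the two-sample interval being the one that decides, as 10.3.7 indicates. The comparison at single counts turns on fractions of a percentage point, so the actual literature count should be checked.

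**What to change.** In 10.1, 10.3.7 and the synopsis, replace the Wald interval for the difference with the Miettinen-Nurminen score interval and leave the -25% comparison as it is. Newcombe is not an equal substitute here, because its error remains about 2.7–2.8% at n = 35 to 40. State the literature numerator, and give the minimum passing responder count for each possible per-protocol size (with 64/82: 22 of 29, 24 of 32, 26 of 36, 29 of 40).

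The change needs SAP wording and one line of code. It does not alter patients, endpoint or margin. The price is power: 5.4 points at n=29 (77.7% to 72.3%), 3.3 at n=36 (83.5% to 80.2%) and 2.7 at n=40 (86.3% to 83.6%). At 29 evaluable patients power against the sampled literature rate is already below the stated 80% with Wald, so the sponsor should see these figures when agreeing the change.

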10.2 Sample size assessment

The sample size is determined in accordance with S.C. Chow, J. Shao, H.Wang. Sample Size Calculations in Clinical Research. London: Taylor&Francis, 2003. – 358 p.

Since the main variable will be expressed as the proportion of patients who responded to therapy with BIOVEN 10%, the sample size was determined based on the possibility of using non-inferior efficacy assessment criteria with a two-sided test at a significance level of α 5%.

Null hypothesis H0: $p-p_0 \le \delta$, where the clinical effectiveness *p*- the proportion of patients who responded to therapy with the drug BIOVEN 10%; *p*₀- proportion of patients responding to therapy according to literature data. δ - the limit of the difference of proportions without clinical significance. An alternative hypothesis H1: $p-p_0 > \delta$.

The sample size in a group when comparing proportions for a study with non-inferiority efficiency is calculated by the formula (Chow, S. C., Wang, H., & Shao, J. (2007). Sample size calculations in clinical research. Chapman and Hall/CRC.):

 $n=(Z_{a/2}+Z_{b/2})^2\times(p\times(1-p))/(p-p_0-\delta)^2$

According to the literature, the effectiveness of IVIG when used in patients with ITP varies between 60-80% [Anurag Singh, Günalp Uzun, Tamam Bakchoul / Primary Immune Thrombocytopenia: Novel Insights into Pathophysiology and Disease Management // J. Clin. Med. 2021, 10, 789. https://doi.org/10.3390/jcm10040789], [Godeau B., Caulier M-T. Decuypere L. et al. Intravenous immunoglobulin for adults with autoimmune thrombocytopenic purpura: results of a randomized trial comparing 0'5 and 1 g/kg b.w. // British Journal of Haematology, 1999, 107, 716-719; Ruqayyah J. Almizraq, Donald R. Branch Efficacy and mechanism of intravenous immunoglobulin treatment for immune thrombocytopenia in adults // Ann Blood 2021;6:2 | http://dx.doi.org/10.21037/aob-20-87; Drew Provan, Roberto Stasi, Adrian C. Newland et al. International consensus report on the investigation and management of primary immune thrombocytopenia // Blood, 14. - Jan 2010, Vol. 115, Number 2]). However, the most similar to this study (in terms of performance evaluation standards and study design) is the 2020 publication. In this publication, the drug administration

| Bioven | Page 70 |
|----------------------------|--------------------------------|
| Trial Code: 2021-BV-ITP-BP | Version 1.4 from July 03, 2023 |

scheme is recommended by the EMA and this Protocol, the total number of patients in the group is 82, the effectiveness of the use of IVIG in the treatment of ITP is indicated - 78% [Parodi E, Russo G, Farruggia P, Notarangelo LD, Giraudo MT, Nardi M, et al. Management strategies for newly diagnosed immune thrombocytopenia in Italian AIEOP Centres: do we overtreat? Data from a multicentre, prospective cohort study. Blood Transfus. 2020;18(5):396.]. According to our data and data from the literature, immunoglobulin belongs to drugs with a highly variable efficiency of 20-25%. Therefore, for a non-inferiority study, we consider it appropriate to set δ (the limit of the difference in efficiency between the obtained and expected results) at the level of -25%.

Thus, for a significance level of 5% and a statistical power of 80%, the effectiveness of the drug in the comparison model reaches 78%, the limit of the difference in specific weights (difference in effectiveness) without clinical significance δ is - 0.25. Then the calculation of the minimum sample size will look like this:

 $n = (1,96+1,28)2 \times (0,78 \times (1-0,78) / (0,78 - 0,78 + 0,25)^2 = 29$

Considering the risk of dropping out of patients for various reasons (20%), 36 patients will be included in the study.

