10.3.7. Conclusion on non-inferiority effectiveness

In accordance with EMA recommendations for clinical studies of immunoglobulin normal for intravenous administration (*Guideline on the clinical investigation of human normal immunoglobulin for intravenous administration (IVIg)*, *EMA/CHMP/BPWP/94033/2007 rev. 4, 16 December 2021)* the obtained results will be compared with literature data The conclusion of non-inferiority of the drug Bioven, solution for infusions 10%, in the treatment of chronic immune thrombocytopenia, will be made according to the main efficacy variable using an approach based on confidence intervals. To do this, the calculated limits of the 95% confidence interval (CI) for the difference in the

percentage of positive results according to the main variable ("the drug is effective") for the studied group must be compared with the limit of the non-inferiority zone - effectiveness that is not inferior (-25%) to the calculated based on data for comparison. If the lower limit of the CI is greater than the

| Bioven | Page 74 |
|----------------------------|--------------------------------|
| Trial Code: 2021-BV-ITP-BP | Version 1.4 from July 03, 2023 |

lower limit of the non-inferiority zone (non-inferiority), then it will be considered that the study drug is not inferior in effectiveness compared to literature data.

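### The 78% benchmark comes from one cohort titled newly diagnosed ITP, but the non-inferiority conclusion is stated for chronic ITP, with no bridge across disease phase, no sensitivity to the benchmark and two alternative rejection rules

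*Combined protocol and SAP*

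**What the plan says.** Section 10.2 quotes a literature range of 60-80% for IVIG in ITP, not stated to be specific to chronic disease. It then settles on one source: "However, the most similar to this study (in terms of performance evaluation standards and study design) is the 2020 publication". The dosing scheme is the other similarity given. The cited title is "Management strategies for newly diagnosed immune thrombocytopenia in Italian AIEOP Centres: do we overtreat", the rate taken is 78%, and Section 10.1 adds: "The number of patients for the portion taken from literature sources is taken from the 2020 publication and will be 82".

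Section 2.1 classes newly diagnosed, persistent and chronic ITP separately. Sections 4.1 and 5.1 admit only chronic primary ITP, at least 12 months from diagnosis. Section 10.3.7 says that the conclusion of non-inferiority "in the treatment of chronic immune thrombocytopenia, will be made according to the main efficacy variable", using the 95% confidence interval for the difference against -25 points. It ends by comparing the drug with literature data.

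On the test itself, Section 10.1 says: "For non-inferiority research, the null hypothesis is rejected if the conditions are met". Two conditions follow, joined by 'or'. The first has no n0 term; the second has one. It also says: "Confidence intervals of the difference will be calculated according to the generally accepted Wald method". Section 10.4 assigns the efficacy analysis to the per-protocol set.

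**The concern.** In a single-arm trial the external rate is the whole comparator, so the conclusion reaches no further than the population that produced the rate. By its title, the reference cohort belongs to one disease phase and the trial enrols another. The reasons given for choosing the source do not mention phase, which is the feature that defines both eligibility and the claim.

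The plan itself shows that the rate is uncertain by quoting 60-80%, yet it fixes one value near the top and plans no analysis at any other. A failed trial could then reflect the benchmark and not the product, and a passed trial would carry a chronic-ITP statement that the cited source, as titled, does not by itself support. In neither case would the report contain a planned analysis to help the reader.

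The 'or' in 10.1 is a related gap: the verdict at a given responder count can depend on which condition is applied, and the plan does not say which decides.

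**Working it through.** **Inputs.** p0 = 0.78 and n0 = 82 (10.1, 10.2); margin -0.25 and two-sided 5%, z = 1.96 (10.2); n = 29 minimum and 36 after dropout (10.2), 40 (4.1); range 60-80% (10.2).

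**1. The plan's own figure.** n = (1.96 + 1.28)² × 0.78 × 0.22 / 0.25² = 10.4976 × 0.1716 / 0.0625 = 28.82, so 29, as stated. Dropout: 29 / 0.8 = 36.25; the plan says 36. This formula has no n0 term; it treats 78% as known.

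**2. The two rejection forms.** The first condition is damaged in the text available. I read it as √n(p − p0 + 0.25)/√(p(1−p)) > 1.96. The Wald form adds p0(1−p0)/82 to the variance. Take 25/36 = 0.6944:

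- Difference from 0.78: -0.0856. Trial variance 0.6944 × 0.3056 / 36 = 0.005894. Reference variance 0.78 × 0.22 / 82 = 0.002093.
- First form: -0.0856 − 1.96 × √0.005894 = -0.236, above -0.25: pass.
- Wald: -0.0856 − 1.96 × √0.007987 = -0.261, below -0.25: fail.
- Wald at 26/36: lower limit -0.229: pass.

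So at n = 36 the minimum pass is 25 or 26. At p0 = 78% the forms differ by one responder at 8 of the 12 denominators from 29 to 40 (all except 29, 32, 37 and 40).

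**3. Minimum responders as p0 varies** (Wald, with n0 = 82 and 25 points kept at every p0, an assumption):

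| p0 | Rate to exclude | n = 29 | n = 36 | n = 40 |
|---|---|---|---|---|
| 60% | 35% | 17 | 20 | 22 |
| 65% | 40% | 18 | 22 | 24 |
| 70% | 45% | 19 | 23 | 26 |
| 75% | 50% | 21 | 25 | 27 |
| 78% | 53% | 21 | 26 | 28 |
| 80% | 55% | 22 | 26 | 29 |

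**4. Chance of passing, exact binomial, n = 36:**

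| True rate | Pass at 78% (26 or more) | Pass at matching p0 |
|---|---|---|
| 53% (null boundary) | 1.5% | – |
| 65% (assumed) | 23% | 75% (22 or more) |
| 70% (assumed) | 47% | 84% (23 or more) |
| 78% | 85% | 85% |

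A pass at 78% implies a pass at the lower p0. The chance that the verdict turns on p0 alone is therefore 75 − 23 = 52% at a true 65%, and 84 − 47 = 37% at a true 70%. Over every n from 29 to 40, the chance of passing at 78% is 19-31% (true 65%), 39-58% (true 70%) and 77-92% (true 78%).

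Under the first form at n = 36 (25 or more) the chance is 3.4% at a true 53% and 92% at a true 78%.

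**5. What a sensitivity row would show.** For 26/36, the Wald lower limits at p0 = 60, 65, 70, 75, 78 and 80% are -0.058, -0.107, -0.155, -0.202, -0.229 and -0.248.

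**The case against.** The sponsor did choose and justify a reference, on grounds that matter. Section 3 and the end of 10.3.7 speak of literature data, and the words about chronic ITP in 10.3.7 can be read as describing the use under study. Section 10.1 already plans "calculate of 95% confidence intervals for proportions and differences of fractions", and p0, n0 and the formula are all given, so a reader could work out any row. Keeping n0 = 82 at 60% or 65% describes no cited study. A descriptive table also leaves the primary verdict, and so the risk of failing at 78%, as it was.

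Much of this stands, and it puts the weight on interpretation. What remains is that phase comparability is not addressed anywhere, and that no interval for the difference is planned at any benchmark but 78%.

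Four stronger readings are tempting, and the documents do not support them:

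- *The 82 patients were all newly diagnosed, or chronic patients respond less well.* Only the title is available. The make-up of the cohort and the direction of any bias cannot be settled, and 65% and 70% are assumed rates.
- *The benchmark favours the drug.* It lies near the top of the quoted range, so it is mostly strict on the product.
- *The test is lenient because a drug truly at 60% passes 9.0% of the time at n = 36.* With p0 = 78% and 25 points the null is 53% or less, so a 60% drug lies inside the margin. The relevant error is 1.5% (Wald) or 3.4% (first form).
- *The plan claims non-inferiority to IVIG in chronic ITP generally.* It does not say so, but its wording leaves room for that inference.

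**Conclusion.** The concern holds as a gap in justification and interpretation, and should be fixed. It is certain from the text that the benchmark rests on one source titled newly diagnosed ITP, that phase is not discussed in choosing it, that the conclusion is stated for chronic ITP, and that no sensitivity to p0 is planned.

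The size is conditional. The six-responder shift in the minimum pass at n = 36 depends on keeping n0 = 82 and the 25-point margin. The loss in the chance of passing also depends on assumed chronic-ITP rates that no document gives. There is no evidence of inflated false acceptance.

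The unresolved 'or' is a separate but real ambiguity. The Wald interval with n0 = 82 is the better-supported reading, since 10.1 prescribes it and 10.3.7 decides on the interval for the difference. However, the sample-size formula, without n0, matches the first form.

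**What to change.** 1. **Section 10.3.7.** Word the conclusion as non-inferiority within 25 points of the 78% rate in the cited 2020 cohort (titled newly diagnosed ITP). Wider wording is open if 10.2 shows that this cohort is comparable with chronic ITP, or if p0 is replaced with chronic-ITP data. If p0 is replaced, restate margin and sample size together.
2. **Section 10.3.3.** Pre-specify one descriptive table of the 95% confidence interval for the difference at p0 = 60, 65, 70, 75, 78 and 80%, at the actual per-protocol n, with n0 = 82 labelled an assumption. State that it aids interpretation, is not a second test, and does not lower the chance of failing at 78%.
3. **Section 10.1.** Name the Wald interval with n0 = 82 as the one deciding form and remove the alternative.

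**Cost.** One table, one sentence and a narrower claim; no change to enrolment unless p0 is replaced. One consequence should be disclosed. Section 10.2 says "Considering the risk of dropping out of patients for various reasons (20%), 36 patients will be included in the study", from a formula without n0. At n = 36 and a true rate of 78%, power is 85% under the Wald interval against 92% under the first form. It can be lower still if the per-protocol count falls below 29, for example 65% at n = 22.
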